6.2 Unblinding

At the initiation of the study, the study site will be instructed on the method for breaking the blind. The unblinding method will use the IWRS process. Using the IWRS will allow the Investigator to have immediate access to the unblinding system.

Unblinding of individual subject treatment by the Investigator should be limited to medical emergencies or urgent clinical situations in which knowledge of the subject's study treatment is necessary for clinical management. In situations where the urgency of the case requires immediate action, investigators should use their best judgment, based on the nature and urgency of the clinical situation, and proceed with unblinding. In emergency situations, the decision to unblind resides solely with the Investigator.

For unblinding, sites at all locations should call the following [REDACTED] Medical Monitor 24/7 global medical coverage hotline:

Medical Monitor 24-Hour Safety Hotline for Protocol Inquiries	
Europe, Middle East and Africa (EMEA) and Asia-Pacific (APAC)	[REDACTED]
United States	[REDACTED]
Latin America	[REDACTED]

Once a subject's treatment assignment has been unblinded for a medical emergency or urgent clinical situation, the [REDACTED] Medical Monitor should be notified within 24 hours of unblinding of

the treatment and should inform the Sponsor's Medical Monitor. Information relating to unblinding (eg, the reason, date) should be clearly recorded in the subject's study file. In addition, the Investigator should consider whether the clinical event that prompted unblinding should be considered an SAE, according to the regulatory definitions or criteria for SAEs, and if so, submit an SAE report as described in Section 9.2.

The [REDACTED] Safety and Risk Management group will also unblind any SAE reports in compliance with regulatory reporting requirements. In addition, Enanta Pharmaceuticals, Inc. may unblind individual subjects at any time for matters relating to safety concerns.

7. STUDY CONDUCT AND VISIT SCHEDULE

7.1 Study Site Visits

Details of assessments at each study site visit are presented in the SoA ([Appendix 1](#)). Study sites will be responsible for following up with subjects for any missed study site visits.

7.1.1 Screening Period (Day-1 to Day 1)

Screening procedures (from Day-1 to Day 1) will occur after the subject signs and dates an institutional review board (IRB)- or ethics committee (EC)-approved ICF and provides authorization to use protected health information (see Section [12.1.3](#)). The ICFs will be completed before conduct of any study-specific procedures.

After signing the ICF, screening assessments will be assessed within 24 hours before dosing. Some procedures performed as part of standard-of-care before Screening may be used in determining study eligibility, such as RSV diagnostic test or safety laboratory tests performed up to 3 days before informed consent and chest imaging performed within 2 days before informed consent, as specified in Section [8](#) and the SoA ([Appendix 1](#)). As required, screening safety laboratory test samples will be sent to the local laboratory for expedited testing.

After signing the ICF, Screening should be completed as soon as possible, and the subject will be randomized and administered the first dose of study drug within 24 hours of signing the ICF.

7.1.2 Treatment Period (Days 1 to 21)

Study Site Visits (Days 1, 4, 7, 11, 16, and 21):

Subjects who meet all of the inclusion criteria and none of the exclusion criteria will be eligible to enter the study and will be randomized 2:1 to receive [REDACTED] EDP-938 or placebo administered orally for 21 days. Subject randomization will be stratified by ribavirin treatment (presence or absence) and ALC (<200 or \geq 200 cells/ μ L). Presence of ribavirin treatment will be defined as \geq 1 dose of ribavirin (oral, intravenous, or aerosolized) before randomization or with written orders for the initiation of therapy at the time of randomization.

The study drug treatment duration is 21 days, during which 6 study visits will be performed.

Randomized subjects will be assigned to an electronic device [REDACTED]

Following randomization on Day 1, subjects must complete baseline assessments before receiving the first dose of EDP-938 or placebo. Although prior local safety laboratory test results may have been used to determine eligibility, separate safety laboratory samples must be collected and sent to the central laboratory for baseline assessment. If Screening and randomization/first dose occur on the same day (Day 1), then screening assessments for vital signs and pulse oximetry will be used as baseline values. If Screening (Day -1) and randomization/first dose

(Day 1) occur on different calendar days within a 24-hour period, then vital signs and pulse oximetry will be performed again on Day 1 (predose).

Subjects will receive the first dose of study drug while at the study site and will be instructed to take EDP-938 or placebo QD at approximately the same time every day (± 1 hour) on each of the 20 subsequent days. The subject will also receive instructions on the appropriate storage and transport of study drug. At each study visit, subjects should bring their study drug with them as part of their study site visit for drug accountability and for dosing of study drug. If a subject is unable to attend a study site visit, a home visit by study site personnel may be arranged, if feasible.

Except for Screening and Day 1 visits, visit assessments for other visits may be completed at the study site or by study site personnel via a home visit, if feasible.

During study visits throughout the Treatment Period, safety assessments, blood collections, and nasopharyngeal swab collections will be conducted as specified in the SoA ([Appendix 1](#)). Safety evaluations will include assessment of clinical laboratory findings, physical examination findings (as applicable), vital sign measurements, pulse oximetry measurements, AEs, and concomitant medications. Other assessments include incidences of hospitalization, ICU admissions or utilization of ICU care for >24 hours, incidences of MAARI, standard of care test results (eg, chest imaging reports, laboratory tests, ECGs), mechanical ventilation, and supplemental oxygen use (≥ 2 L/min for >24 hours).

All study assessments during the Treatment Period are detailed in the SoA ([Appendix 1](#)).

7.1.3 Follow-up Period (Days 22 to 49)

Study Site Visits (Days 28 and 49):

Follow-up visits will occur 1 and 4 (EOS visit) weeks after the last dose of study drug for all subjects including those who discontinue treatment early (ie, before completing 21 days of dosing). Visit assessments may be completed at the study site or by study site personnel via a home visit, if feasible.

All study assessments during the Follow-up Period are detailed in the SoA ([Appendix 1](#)).

Any subject with ongoing AEs/SAEs at the EOS visit should be followed up until resolution of their AE/SAE or until the Investigator has determined that the event has stabilized as discussed in Section [9.3](#).

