2.2.2 Secondary Endpoints

- Change in RSV RNA viral load from Baseline through Day 49 in nasopharyngeal swab samples by RT-qPCR
- Incidence of subjects who develop respiratory failure of any cause requiring mechanical ventilation (invasive or noninvasive) or all-cause mortality through Day 49
- Incidence of subjects with RSV RNA viral load below the limit of detection in subjects receiving EDP-938 through Day 49
- Time to RSV RNA viral load below the limit of detection
[REDACTED]
- Plasma PK concentrations of EDP-938 and [REDACTED]
[REDACTED]
- Safety endpoints include, but are not limited to, AEs, serious adverse events (SAEs), vital sign measurements, pulse oximetry measurements, and clinical laboratory test results (including chemistry, hematology, and urinalysis)

2.2.3 [REDACTED]

[REDACTED]
[REDACTED]
[REDACTED]
[REDACTED]
[REDACTED]
[REDACTED]
[REDACTED]

1

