4. STUDY DESIGN

This is a Phase 2, randomized, double-blind, placebo-controlled, multicenter study evaluating the efficacy and safety of EDP-938 in HCT recipients with acute RSV infection and symptoms of URTI.

The study has 3 periods:

- Screening Period will occur from Day -1 to Day 1. During this period, subjects will review and sign the ICF. Subjects will undergo screening assessments. Screening should be completed as soon as possible, and the subject will be randomized and administered the first dose of study drug within 24 hours of signing the ICF. A subject will be considered enrolled at the time of randomization.
- Treatment Period will begin with the first dose of study drug on Day 1 and will conclude with the End-of-Treatment (EOT) Visit on Day 21.
- Follow-up Period for safety will begin following the last dose of study drug and will conclude at the End-of-Study (EOS) visit on Day 49, 28 days following the last dose of study drug.

The end of the study will be defined as the last visit of the last subject enrolled.

[figure not shown]

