7.2.2 Procedures for Early Discontinuation or Early Termination of Treatment

Subjects who discontinue treatment before completing 21 days of dosing should return to the study site within 24 hours after the last dose of study treatment to complete an EOT visit, including EOT PK sample collection. Subjects should then return to the clinic for the Follow-up Visit 1 (EOT + 1 week) and the EOS visit 4 weeks following the last dose of the study drug.

Subjects who discontinue the study before Day 28 should return to the site within 48 hours to complete Follow-up Visit 1 (EOT + 1 week) procedures. Subjects who discontinue the study early between Day 28 and Day 49 should return to the study site within 48 hours to complete the EOS procedures (see [Appendix 1](#)). Any subject who withdraws with ongoing AEs/SAEs should be followed until resolution of their AE(s) or until the Investigator has determined that the AE(s) has stabilized.

Site staff will attempt to contact any subject who does not return to the site for the EOS visit at least three times using the subject's preferred method of communication, followed by a letter requiring delivery notification if the three attempts were unsuccessful. Any subject who still cannot be reached following those attempts will be considered lost to follow-up. These subjects will be included in the PK and safety analysis as indicated in Section [11.3](#).

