RSV viral load by both RT-qPCR and CRIA:

Analysis Visit #	Analysis Visit Label	Target Day	Derivation
1	Day 1	1	Based on nominal visit of V1
4	Day 4	4	Based on nominal visit of V2
7	Day 7	7	Based on nominal visit of V3
11	Day 11	11	Based on nominal visit of V4
16	Day 16	16	Based on nominal visit of V5
21	Day 21	21	Based on nominal visit of V6 if subject completes treatment
28	Day 28	28	Based on nominal visit of FU V1 if subject completes treatment and last visit is FU V2.
49	Day 49	49	Based on nominal visit of FU V2 if subject completes treatment and study
97	Early Disc/EOT	NA	Based on nominal visit of V6 if subject discontinues treatment
98	Early Disc/FU1	NA	Based on nominal visit of FU V1 if subject discontinues treatment or last visit is FU V1.
99	Early Disc/FU2	NA	Based on nominal visit of FU V2 if subject discontinues treatment or study.

ECG:

Analysis Visit #	Analysis Visit Label	Target Day	Derivation
-1	Screening	-1	Based on nominal visit of Screening
4	Day 4	4	Based on nominal visit of V2
11	Day 11	11	Based on nominal visit of V4
21	Day 21	21	Based on nominal visit of V6 if subject completes treatment.
28	Day 28	28	Based on nominal visit of FU V1 if subject completes treatment and last visit is FU V2.
97	Early Disc/EOT	NA	Based on nominal visit of V6 if subject discontinues treatment
98	Early Disc/FU1	NA	Based on nominal visit of FU V1 if subject discontinues treatment or last visit is FU V1.

PK:

Analysis Visit #	Analysis Visit Label	Target Day	Timepoint* Assessment	Derivation
1	Day 1	1	1	Based on nominal visit of V1
1	Day 1	1	2	Same as above
4	Day 4	4	1	Based on nominal visit of V2
7	Day 7	7	1	Based on nominal visit of V3
7	Day 7	7	2	Same as above
11	Day 11	11	1	Based on nominal visit of V4
16	Day 16	16	1	Based on nominal visit of V5

21	Day 21	21	1	Based on nominal visit of V6 if subject completes treatment
21	Day 21	21	2	Same as above
97	Early Disc/EOT	NA		Based on nominal visit of V6 if subject discontinues treatment

* On Day 1, Day 7, and Day 21, two plasma PK samples will be collected (one predose and one postdose) and thus are assigned as Timepoint 1 and 2. At all other visits, only predose samples will be collected.

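### The final visit follows the last dose, so subjects who stop drug early are scheduled to be observed only to Day 29–48, short of the Day 49 horizon of three secondary endpoints

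*Protocol*

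**What the plan says.** Section 7.1.3 sets the two follow-up visits 1 and 4 "weeks after the last dose of study drug for all subjects including those who discontinue treatment early". Section 7.2.2, the protocol summary and Schedule of Assessments footnote b repeat the rule; in Section 7.2.2 an early stopper returns for "the EOS visit 4 weeks following the last dose of the study drug".

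Elsewhere the same visit has a fixed day. Section 4 refers to the "End-of-Study (EOS) visit on Day 49, 28 days following the last dose of study drug", and the visit line in Section 7.1.3 names Days 28 and 49.

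Section 2.2.2 defines the endpoints by study day. They include the incidence of "respiratory failure of any cause requiring mechanical ventilation (invasive or noninvasive) or all-cause mortality through Day 49" and "Change in RSV RNA viral load from Baseline through Day 49 in nasopharyngeal swab samples by RT-qPCR". The incidence of viral load below the limit of detection has the same horizon.

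After EOS, Section 9.2.5 requires reporting only of SAEs considered related to study drug, deaths included. Sections 7.1.3 and 9.3 continue follow-up of adverse events already ongoing.

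In the SAP viral-load table (Section 4.4.1), analysis Day 49 exists only for subjects who complete both treatment and study. For others the last visit becomes Early Disc/FU2, "Based on nominal visit of FU V2 if subject discontinues treatment or study". Early-discontinuation visits are left out of by-visit summaries. Section 8.2.1 scales the viral-load AUC by 49/t_last. Section 12 deletes the respiratory-failure/mortality endpoint and keeps the data as listings.

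**The concern.** The endpoint clock starts at Day 1, while the observation clock for early stoppers starts at their last dose. The two agree only when dosing runs to Day 21. No section requires a Day 49 check of vital status or ventilation after an earlier EOS.

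The shortfall is unlikely to be random. Section 7.2.1 lists adverse events and lack of efficacy among the reasons for discontinuation, and Section 5.8 ends dosing when certain azoles become medically necessary. Subjects doing badly may therefore be watched for the shortest time. An all-cause endpoint would then lose unrelated deaths and ventilations in that group. If stopping differed between arms, the Day 49 comparison planned in the protocol could be biased, and blinding would not prevent it.

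**Working it through.** **Inputs.** Treatment lasts 21 days (Section 7.1.2: "The study drug treatment duration is 21 days, during which 6 study visits will be performed"), so an early stopper's last dose falls on Day L = 1 to 20. The visits are at L+7 and L+28 (Sections 7.1.3 and 7.2.2). The horizon is Day 49 (Section 2.2.2). The EOS window is ±2 days (Appendix 1).

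**The plan's own figure.** With L = 21 the visits fall on 21+7 = Day 28 and 21+28 = Day 49. The stated days reproduce for subjects who complete dosing.

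**Early stoppers.** EOS day = L+28, and days short = 49 − (L+28) = 21 − L. For the illustration, assume a constant hazard and a true Day 49 risk of 30% in early stoppers. Then observed risk = 1 − 0.7^((L+28)/49), and missed share = (30% − observed)/30%. The SAP sets Day 1 to time 0, so a sample on the EOS target day has t_last = L+27. The last column assumes that off-schedule follow-up samples enter the AUC.

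| Last dose | FU1 | EOS | Days short | Observed risk | Missed share | 49/t_last |
|---|---|---|---|---|---|---|
| Day 1 | Day 8 | Day 29 | 20 | 19.0% | 37% | 1.75 |
| Day 7 | Day 14 | Day 35 | 14 | 22.5% | 25% | 1.44 |
| Day 14 | Day 21 | Day 42 | 7 | 26.3% | 12% | 1.20 |
| Day 20 | Day 27 | Day 48 | 1 | 29.5% | 2% | 1.04 |
| Day 21 | Day 28 | Day 49 | 0 | 30.0% | 0% | 1.02 |

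Applying the ±2-day window, early stoppers' EOS can fall from Day 27 to Day 50.

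**Trial level.** The documents give no rate of early treatment discontinuation. Assume 5% to 30% of the 190 planned subjects, stopping uniformly over Days 1–20 (mean shortfall 10.5 days). That is 10 to 57 subjects and about 100 to 600 unobserved person-days. At the mean shortfall, observed risk in stoppers is 1 − 0.7^(38.5/49) = 24.4%, which is 5.6 points low. Weighted by the share stopping, the overall rate is low by 0.05 × 5.6 = 0.3 to 0.30 × 5.6 = 1.7 points; at 10% stopping it is 0.6.

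**AUC.** Assume log10 load falls linearly from 7 to 0 over 14 days.
- Completer, sampled at t = 0, 3, 6, 10, 15, 20, 27, 48: trapezoid AUC 50.0, times 49/48 = 51.0.
- Day 7 stopper with the same viral course, sampled at t = 0, 3, 6, 13, 34: AUC 54.0, times 49/34 = 77.8.

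The excess comes mainly from the scaling, which spreads the earlier, higher-load period over the unobserved tail. Sparser sampling adds a little.

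**The case against.** The strongest reply is that the gap is narrower than it looks.

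- **Capture.** A reader might infer that every death, ventilation or viral rebound after an early EOS is lost. The documents do not support that for clinical events. Events ongoing at EOS are followed until resolution, death or stabilisation (with a 30-day limit on the last), or until alternative therapy begins. Drug-related SAEs after EOS must be reported. This partly covers a subject whose adverse event is still active at EOS. Not covered are new events, unrelated to study drug, that start between EOS and Day 49.
- **Primary endpoint.** A reader might infer that LRTC is affected. It runs through Day 28, and the earliest target EOS is Day 29. Only a Day 1 stop seen at the early edge of the window (Day 27) falls short.
- **This trial's report.** A reader might infer that reported Day 49 event rates or treatment comparisons are biased. SAP Section 12 deletes the respiratory-failure/mortality endpoint and withholds tests and treatment-difference estimates; Section 4.1 records 9 subjects randomised. That consequence belongs to the protocol's plan alone.
- **AUC.** The SAP does address unequal follow-up by scaling. This stands as an attempt, but the scaling is not neutral, as the working shows.
- **Purpose of the visits.** Section 4 describes follow-up as being for safety, which explains counting from the last dose. This stands. Moving both visits to fixed Days 28 and 49 would give up the post-dose contacts, and a Day 1 stopper would then have no scheduled visit between end of treatment and Day 28.

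**Conclusion.** The mismatch is real and follows directly from the protocol text: scheduled observation of early stoppers ends 1 to 20 days before the horizon of three secondary endpoints, with no required capture of new, unrelated events in between. Because stopping can depend on illness, the shortfall is potentially informative and could bias the planned Day 49 comparison. That comparison is secondary; the primary endpoint is sound on target days.

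The day counts rest on the documents alone. The 12% to 37% does not: it applies only to early stoppers (Day 14 to Day 1) and assumes both the 30% risk and the constant hazard. If events cluster early in an acute infection, the missed share is smaller. It should not be read as an expected loss for the trial.

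Under the SAP the remaining effect is descriptive: no analysis Day 49 viral load for early stoppers, their off-schedule visits absent from by-visit tables, and AUCs resting on extrapolation. The protocol wording should be corrected, but nothing here undermines the main analysis.

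**What to change.** Keep the end-of-treatment visit and both post-last-dose safety visits. Add to Sections 7.1.3 and 7.2.2 and Schedule of Assessments footnote b that every randomised subject, whatever the date of last dose, has vital status and mechanical ventilation recorded at study Day 49 by telephone or record check, with a nasopharyngeal swab where feasible. The limit in Section 7.2 on subjects who withdraw consent for further information still applies. Reconcile the fixed-day wording in Sections 4 and 7.1.3 with the last-dose rule. In any later SAP, assign a Day 49 swab to analysis Day 49 whether or not treatment was completed; otherwise the added sample would still be left out.

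The cost is one brief extra contact for each early stopper. The sample size is unchanged, since it rests on the Day 28 endpoint.

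For the report of the terminated trial, state each subject's last observed day and flag any Day 49 listing or AUC that rests on shorter follow-up. Carry the corrected wording into any later protocol that reuses this schedule.

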7.2 Subject Withdrawal/Early Termination/Completion

Subjects will be considered to have completed treatment if they did not permanently discontinue treatment before the EOT visit. Subjects will have completed the study if they completed the full Treatment Period and full Follow-up Period.

If a subject withdraws from the study and also withdraws consent for disclosure of future information, no further evaluations should be performed and no additional data should be

collected. Enanta Pharmaceuticals, Inc. may retain and continue to use any data collected before such withdrawal of consent.

Any randomized subjects who withdraw or are withdrawn from the study will not be replaced.

7.2.1 Withdrawal Criteria

Reasons for discontinuation include but are not limited to the following:

- AE
- Lack of efficacy
- Lost to follow-up
- Withdrawal by subject
- Protocol deviation (including noncompliance with study drug or study procedures)
- Pregnancy
- Study terminated by the Sponsor
- Other

7.2.2 Procedures for Early Discontinuation or Early Termination of Treatment

Subjects who discontinue treatment before completing 21 days of dosing should return to the study site within 24 hours after the last dose of study treatment to complete an EOT visit, including EOT PK sample collection. Subjects should then return to the clinic for the Follow-up Visit 1 (EOT + 1 week) and the EOS visit 4 weeks following the last dose of the study drug.

Subjects who discontinue the study before Day 28 should return to the site within 48 hours to complete Follow-up Visit 1 (EOT + 1 week) procedures. Subjects who discontinue the study early between Day 28 and Day 49 should return to the study site within 48 hours to complete the EOS procedures (see [Appendix 1](#)). Any subject who withdraws with ongoing AEs/SAEs should be followed until resolution of their AE(s) or until the Investigator has determined that the AE(s) has stabilized.

Site staff will attempt to contact any subject who does not return to the site for the EOS visit at least three times using the subject's preferred method of communication, followed by a letter requiring delivery notification if the three attempts were unsuccessful. Any subject who still cannot be reached following those attempts will be considered lost to follow-up. These subjects will be included in the PK and safety analysis as indicated in Section [11.3](#).

7.2.3 Documentation of Withdrawal of Subjects

The reason for early withdrawal/termination/lost to follow-up of any subject from the study must be documented in source and on the appropriate eCRF. If the reason for early withdrawal is an

AE or an abnormal laboratory value, the specific event or test result, if available, should be recorded on the AE eCRF and the subject should be monitored until the event is resolved or deemed stable by the Investigator.

